### **3 STUDY POPULATION AND STUDY PROCEDURES**

#### **3.1 Inclusion and exclusion criteria, justification of study population**

As the aim of the study is to improve psychotherapeutic treatment in the acute phase of psychosis, the inclusion of patients suffering from this disorder is necessary and cannot be studied in healthy people.

We will recruit newly admitted inpatients from the Psychiatric University Hospital with a diagnosis of a psychotic spectrum disorder (schizophrenia, schizoaffective disorder, acute psychotic

disorder, psychosis not otherwise specified, bipolar disorder with psychotic features, major depression with psychotic features). Patients are recruited within the first three days of hospitalization to test psychotherapeutic interventions in the acute phase of illness.

Patients fulfilling all of the following inclusion criteria may be enrolled in the study:

- Informed consent as documented by signature
- Male and female patients from PUK inpatient units between 18 and 65 years of age
- ICD-10 diagnosis of psychosis (F2) meeting DSM-IV criteria
- Fluent in German and able to understand the instructions

The presence of any one of the following exclusion criteria will lead to exclusion of the participant:

- Organic schizophrenia-like disorder (ICD: F0.6)
- Cognitive impairments: strongly below average values in more than two cognitive tests (percentage rank < 5)
- Drug or alcohol abuse during treatment
- Previous enrolment in the current study
- Enrolment of the investigator, his/her family members, employees and other dependent persons.
- During study: Complete stop of taking antipsychotic medications without the consent of the attending physician.

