### 3.4 Withdrawal and discontinuation

Participants have the right to abort the study at any point and without providing a reason. The principal investigator and the co-investigator have the right to withdraw participants if they knowingly provide incorrect information, withdraw consent, do not adhere to protocol requirements (i.e. missing appointments, ignoring instructions) or if the disease has progressed (see exclusion criteria).

If participants do not finish the experiment, the data will be stored properly and taken into analysis as far as possible and useful. Additional participants will be recruited to replace the withdrawn participants.

Since they are inpatients, there is a very low risk of missed appointments. If this is still the case, the appointments can be made up on the following day.

If participants are discharged before the end of the study, they may attend the remaining appointments as outpatients if the majority of the study has already taken place (at least 3 psychotherapy sessions must have taken place during inpatient treatment).

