Sample size justification: Comparable studies found effect sizes that were moderate (Cohen's  $d = 0.3 - 0.5$ ). An effect sizes of  $f = 0.25$  will require us to recruit at least 64 patients per group to achieve 80% power and to detect such an effect with reasonable certainty at an alpha level of 0.05. We therefore plan to include a minimum of  $N = 128$  patients (calculated with G\*Power 3.1).

Analysis population: There is only one analysis population for all hypothesis. For inclusion criteria see chapter 4.1.

Analysis of gender differences: Analyses of gender differences are not planned because there is no research evidence to suggest that gender may be a determining variable. However, it is planned to conduct a group comparison between patients who benefit strongly from MI and those who benefit little, and to investigate possible discriminatory factors as part of this.

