#### 4.2. Handling of missing data and drop-outs

All patients who completed the study will be taken into analysis. All collected data will be checked at each study assessment, and missing data will thus be avoided as much as possible. If missing data nevertheless does occur, data has to be excluded.

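### Patients who stop antipsychotics are excluded after randomisation although adherence is a primary endpoint, and the plan analyses completers with no all-randomised analysis

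*Combined protocol and SAP*

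**What the plan says.** Section 2.2 names two primary endpoints: therapeutic alliance (STAR) and adherence (BARS). Section 3.3 describes BARS as rating the share of doses taken over the past month, from 0 to 100%.

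Section 3.1 opens its exclusion list with "The presence of any one of the following exclusion criteria will lead to exclusion of the participant" and ends it with "During study: Complete stop of taking antipsychotic medications without the consent of the attending physician". In Table 2 (section 3.3), randomisation is at visit 1, the eligibility check is at visit 2 (day 0), the sessions are at visits 3 to 6, and the post-measurement is at day 10.

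Section 3.4 lets the principal investigator and co-investigator withdraw participants who, among other grounds, "do not adhere to protocol requirements (i.e. missing appointments, ignoring instructions) or if the disease has progressed (see exclusion criteria". On those who leave, it says "If participants do not finish the experiment, the data will be stored properly and taken into analysis as far as possible and useful", and then "Additional participants will be recruited to replace the withdrawn participants".

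Section 4.1 says "There is only one analysis population for all hypothesis" and refers the reader to inclusion criteria in chapter 4.1. Section 4.2 says "All patients who completed the study will be taken into analysis" and "If missing data nevertheless does occur, data has to be excluded".

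**The concern.** Randomisation makes the two arms comparable only if the patients compared are those randomised, or a subset chosen independently of what happened after allocation. Here a patient can be removed for an event that happens during treatment and is a bad outcome on a primary endpoint. Withdrawal for missed appointments, ignored instructions or progression adds further removals that may depend on arm and outcome.

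The bias can run either way. If MI keeps some patients on medication who would otherwise have stopped, the control arm loses its worst adherers and part of the benefit disappears from the comparison. If MI sessions lead some patients to stop or withdraw, that harm disappears instead. Replacement refills the arm with patients who did not have the event.

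All hypotheses share the one population, so STAR, PANSS, FPTM and GSE are exposed as well. The wording on non-finishers also leaves the choice of data open. Section 7.1 has interim data shown to the Sponsor-Investigator at regular intervals, and the blinding in sections 2.3 and 3.3 covers patients and raters, not whoever decides on withdrawal or on what is useful.

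**Working it through.** **1. Who is analysed, reading the sections together.**
- 3.1: an unauthorised complete stop leads to exclusion. Table 2 puts allocation before any such stop.
- 3.4: withdrawn patients are replaced. Non-finishers' data may or may not be used, with no rule for deciding.
- 4.1: there is one population. Its pointer to chapter 4.1 finds no criteria there. If 3.1 was meant, it leads to the section that contains the stop rule.
- 4.2: completers are analysed and missing data are dropped.
- 4.1 specifies an ANCOVA of the post-value on the baseline value. A patient without a day-10 value drops out of it, and no section says that day-10 measures are sought after exclusion.

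The operative analysis is therefore a completer analysis with a discretionary margin. The progression ground in 3.4 points to the exclusion criteria, but 3.1 lists no progression criterion.

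**2. The plan's own figure.** Section 4.1 gives 64 per group for f = 0.25, 80% power and two-sided alpha 0.05. With noncentrality f² × N = 0.0625 × 128 = 8.0 and one covariate, the F test has 80.1% power, so N = 128 reproduces. It is not in dispute. Replacement protects this count but not the comparability of the arms.

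**3. Size of the bias on BARS (illustration).** The documents give no stopping rates or BARS means, so these inputs are assumed: BARS 80 for everyone who does not stop, in both arms; one month taken as 30 days; accurate recall; all stoppers in an arm stop on the same day and are removed from the completer set. The day-10 assessment (±1 day) is from Table 2.

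A stopper's score is 80 × (1 − days off / 30):
- stop on day 0: 80 × (1 − 10/30) = 53.3
- stop on day 5: 80 × (1 − 5/30) = 66.7

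All-randomised difference (MI minus control) = 80 × (assessment day − stop day)/30 × (control rate − MI rate):

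| Stop rate, control vs MI | Stop on day 0 | Stop on day 5 |
|---|---|---|
| 10% vs 5% | 80 × 10/30 × 0.05 = 1.33 | 80 × 5/30 × 0.05 = 0.67 |
| 15% vs 7.5% | 80 × 10/30 × 0.075 = 2.00 | 80 × 5/30 × 0.075 = 1.00 |
| 20% vs 10% | 80 × 10/30 × 0.10 = 2.67 | 80 × 5/30 × 0.10 = 1.33 |

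Among completers the difference is 0 in every row. That follows from giving all non-stoppers the same mean; it shows what the analysis would miss and is not a separate result. For 15% vs 7.5%, assessment at day 9 or day 11 gives 1.8 or 2.2 points (day-0 stop) and 0.8 or 1.2 points (day-5 stop). Reversing the rates between arms reverses every sign.

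A simulation with 64 per arm, BARS drawn from a normal distribution with mean 80 and SD 15 clipped to 0–100, and 20,000 runs gave 1.33 / 0.66, 1.97 / 1.00 and 2.64 / 1.33 points for all randomised patients, and −0.02 to 0.01 among completers. This confirms the arithmetic but not the assumed inputs.

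At the assumed SD of 15, the middle row is 1.00/15 = 0.07 to 2.00/15 = 0.13 SD, against the planned d = 2f = 0.5.

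**The case against.** Read literally, no sentence says that only completers are analysed. Section 4.2 says completers are included, 3.4 allows non-finishers' data in, and excluding a participant is not the same as discarding that participant's data. On that reading the passages are compatible and the fault is only a loose definition. In addition, the rule covers only a complete stop without the physician's consent. Patients are inpatients for about two weeks, missed sessions can be made up the next day, and the early-discharge clause keeps some patients who would otherwise be lost. The pointer to chapter 4.1 is probably a numbering slip for 3.1. The illustration is small and wholly assumed, and this is a self-described pilot.

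Several of these points stand. The size on BARS is modest, the 4.1 pointer is editorial, and the retention measures reduce loss. Nothing shows an intention to select data after seeing them.

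The compatible reading does not rescue the plan, however. A test of what is possible and useful is not a rule. Outcomes that are never sought after exclusion cannot be recovered later. An ANCOVA that drops missing post-values is in effect a completer analysis, whatever the population is called. The retention measures concern missed visits and early discharge, not removal for stopping medication.

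**Conclusion.** The concern holds and should be fixed before the analysis. Followed as written, the plan makes its primary comparison depend on a post-randomisation event that is part of a primary outcome, replaces the patients removed, and defines no analysis of everyone randomised in their allocated arm. This is an error in the analysis set, not just a missing detail.

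The direction of the bias is unknown. Under the stated assumptions, with stopping twice as common in control as under MI, the completer analysis misses about 0.7 to 2.7 BARS points at day 10; with the rates reversed it flatters MI by the same amount. No figure is available for STAR or the secondary endpoints. The severity rests on an analysis set that is outcome-related and not fixed in advance, and would be the same if the BARS figure were smaller.

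**What to change.** **Analysis set (4.1, 4.2).** Define the primary analysis as all randomised patients in their allocated arm. Because Table 2 checks eligibility after randomisation, a patient found ineligible at visit 2 may be left out only on criteria fixed before any session and judged without knowledge of allocation.

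**Follow-up (3.1, 3.4).** State that a during-study stop or withdrawal from sessions does not remove the patient from the data set, that day-10 assessments including BARS are still sought unless consent to follow-up is withdrawn, and that patients who are replaced stay in the analysis.

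**Missing outcomes (4.2).** Use multiple imputation or a likelihood-based model that includes baseline values and recorded medication status. Add a sensitivity analysis for outcomes missing because of stopping, and keep the completer analysis as a further sensitivity analysis.

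**Consistency.** Reconcile 3.1, 3.4, 4.1 and 4.2. Correct the pointer to chapter 4.1, and either define the progression ground or remove its reference to the exclusion criteria. None of this sets a clinical rule on medication; it concerns only whose data are collected and analysed.

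**Cost.** Revised wording, day-10 assessments for some patients who leave the sessions early, and modest extra analysis. The estimated effect may become smaller or larger.

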### **3.2 Recruitment, screening and informed consent procedure**

Recruitment of patients will take place at the Psychiatric University Hospital Zurich in the form of ongoing recruitment by the study coordinator in the clinical setting as well as by other physicians and psychologists at the hospital. The study is presented and reminded to them in regular intervals at internal clinic reports.

The investigators will explain to each participant the nature of the study, its purpose, the procedures involved, the expected duration, the potential risks and benefits and any discomfort it may entail. Each participant will be informed that the participation in the study is voluntary and that he or she may withdraw from the study at any time and that withdrawal of consent will not affect his or her subsequent medical assistance and treatment.

The participant will be informed that his or her medical records may be examined by authorised individuals other than their treating physician.

All participants for the study will be provided a participant information sheet and a consent form describing the study and providing sufficient information for participant to make an informed decision about their participation in the study. Enough time (one to five days) will be given to the participant to decide whether to participate or not.

The formal consent of a participant, using the approved consent form, will be obtained before the participant is submitted to any study procedure.

The consent form will be signed and dated by the investigator or his designee at the same time as the participant sign. A copy of the signed informed consent will be given to the study participant. The consent form will be retained as part of the study records. The informed consent process must be documented in the patient file and any discrepancy to the process described in the protocol must be explained.

In the case of incapacity to judge or if there is doubt about the capacity to judge, a separate procedure takes place:

The study information must be explained verbally to the interested patient in any case. Handing over the written study information alone is not sufficient. The patient should be able to describe in general terms what participation in the study entails and what the patient's rights are.

If there are doubts about the patient's ability to judge, either because he/she is unable to reproduce what is contained in the study information, or because of critical comments by the health

care personnel and/or trusted persons of the patient, an evaluation is carried out using the "U-Doc" (Hermann et al., 2020; Trachsel & Biller-Andorno, 2022). The information for this is collected on an interdisciplinary basis and discussed with the patient's legal representative and/or a close confidant. Any conflicts of interest in the evaluation can be critically reflected upon and transparently documented in U-Doc. Both the patient and his/her representative have the right to inspect this documentation at any time and can also refuse it.

If an incapacitated person explicitly wishes to participate in the study, we will conduct a detailed information session about the study, at which not only the patient but also the legal representative must be present. It is desirable to have a conversation on site, in exceptional cases the conversation can take place by telephone conference. If there is no legal representative, the law prescribes a cascade of possible representatives (spouse, partner, offspring, parents, siblings). The conversation is recorded (in the CRF). The documentation of the conversation is accessible to the patient and her representative at all times. It is important to note that incapacity is relevant in relation to the decision on medical measures.

Participants will receive financial compensation after completing the study (after post-measurement). A payment of 40 swiss francs per participant is calculated in the budget.

**3.3 Study procedures**

[figure not shown]
Time schedule

The study will last from October 2022 to September 2023.

- From October to December 2022, the study will be planned, and the ethics application will be written and submitted.
- From January, the concrete preparations will take place and
- from February 2023, the implementation will take place. The survey phase will last until August 2023.
- From August to October 2023, the study is to be evaluated, completed and the data analysed.

As can be seen in Table 2, the duration for each patient is between 13 and max. 16 days during their inpatient stay. The goal is to start with the study intervention as soon as possible after entering the psychiatric hospital.

Table 1: Study Flow Chart

**Table 2:** Overview study procedure

\* If questions / need for feedback occur after the last visit, an additional visit shall be provided

	Re-cruitment	Pre-Measurement	Intervention phase				Post-Measurement	
Visits	1 max. 30min.	2 max. 60min.	3 25- 40min .	4 25- 40min .	5 25- 40min .	6 25- 40min .	7 max. 60min.	Follow up max. 60min.
Time (days)	-3 +/-2d	0	2 +/-1d	4 +/-1d	6 +/-1d	8 +/-1d	10 +/-1d	60 +/-5d
Check with treating physician or psychologist	x							
Patient Information and Informed Consent	x							
Randomization	x							
Demographics and information about current treatment	x							
Examination of symptoms with PANSS and MATRICS		x					x	x
Control of In- and Exclusion Criteria		x						
Measurements of secondary outcome variables		x					x	
MI-Intervention (intervention group) or supportive conversations (controls)			x	x	x	x		
Possibility for patients to ask questions and give a feedback							x*	

Detailed description of the planned intervention

Motivational Interviewing is a technique that aims in particular to promote intrinsic motivation and to make ambivalences visible and reduce them. It involves a therapeutic attitude based on the humanistic approach as well as on person-centred psychotherapy according to Carl Rogers. The original founders of MI defined five basic principles: 1. make clear, consensual agreements, 2. show empathy, 3. develop the will to change and clarify discrepancies, 4. redirect resistance, 5. promote self-confidence and responsibility. In addition, MI compliant skills such as active listening, supporting positive behaviours, asking open-ended questions, summarizing and reflecting, supporting self-motivating statements are applied. The concept of MI is that the conversation with the patient goes through different phases of decision making and motivation building. The therapist always addresses and emphasizes the patient's stated desires, reasons, or abilities to change. This is called "change talk." In the same way, however, doubts and counterarguments are also addressed ("sustain talk") and appreciated. The aim is to increase the patient's

discrepancy in a trustworthy and empathic way, so that he or she moves on to the phase of actual decision-making and finally to goal-directed behaviour on the basis of self-developed arguments.

Four interviews will be conducted using this method as part of the study intervention. The content of these will be about participation in treatment. In order to make the intervention measurable, the conversations will be recorded on an audio device and subsequently evaluated by two independent raters according to the number of MI principles and techniques applied.

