## **2 STUDY OBJECTIVES AND DESIGN**

### **2.1 Hypothesis and Objectives**

The **primary objective** of the study is to investigate the impact of a brief intervention with Motivational Interviewing in an acute psychiatric inpatient setting on factors that impact treatment outcome such as therapeutic alliance and adherence to treatment.

The **second objective** is to examine if the effect of Motivational Interviewing can be measured in changes in symptom severity.

The **third objective** is to examine secondary effects of Motivational Interviewing on motivation for further psychotherapeutic treatment and higher expectations of self-efficacy after discharge from the hospital.

Therefore, the study grounds on three **hypotheses**:

1. Four sessions of psychotherapeutic intervention with motivational interviewing for newly admitted acute patients improves the therapeutic alliance and the adherence for treatment compared to supportive counseling.
2. Four sessions of psychotherapeutic intervention with motivational interviewing for newly admitted acute patients decreases symptom severity compared to supportive counseling.
3. Patients show higher motivation to seek psychotherapeutic treatment and have a higher self-efficacy expectation after leaving the inpatient stay, when they received an intervention with motivational interviewing compared to supportive counseling.

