### **2.2 Primary and secondary endpoints**

Primary endpoints are the therapeutic alliance as assessed with the *Scale to Assess Therapeutic Relationship STAR* (McGuire-Snieckus et al., 2007) and adherence to treatment as measured with the *Brief Adherence Rating Scale BARS* (Byerly et al., 2008). These variables will be measured before and after the study intervention or control intervention.

Secondary endpoints include changes in symptom severity as assessed with the *Positive and*

*Negative Symptom Scale PANSS* (Kay et al., 1987), as well as the motivation for psychotherapy (measured with the German version of the *Questionnaire to measure the motivation for psychotherapy* by Schulz et al., 1995) and self-efficacy (measured with the *General Self-Efficacy Scale* by Schwarzer & Jerusalem, 1995). All secondary variables will be measured before and after the study intervention or control intervention.

As this study (risk category A) does not include drugs or other medical products and patients are hardly exposed to any more risks than in routine clinical care, no safety endpoints are defined.

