## 4 STATISTICS AND METHODOLOGY

### 4.1. Statistical analysis plan and sample size calculation

Hypothesis 1: Four sessions of motivational interviewing for newly admitted acute patients (within the first 7 days of hospitalization) improve the therapeutic alliance and the adherence for treatment compared to supportive counseling.

Statistical analysis for hypothesis 1: To apply the statistically most sensitive test, we will use an ANCOVA to analyze the treatment effect of motivational interviewing compared to supportive counseling, with baseline values used as covariates.

Hypothesis 2: Four sessions of motivational interviewing for newly admitted acute patients decreases symptom severity compared to supportive counseling.

Statistical analysis for hypothesis 2: We will use an ANCOVA to analyze the treatment effect of motivational interviewing compared to supportive counseling, with baseline values used as covariates.

Hypothesis 3: Patients show higher motivation to seek psychotherapeutic treatment and have a higher self-efficacy expectation after leaving the inpatient stay, when they received an intervention with motivational interviewing compared to supportive counseling.

Statistical analysis for hypothesis 3: We will use an ANCOVA to analyze the treatment effect of motivational interviewing compared to supportive counseling, with baseline values used as covariates.

Additional calculations: We also want to investigate how the number of hospitalization days and the severity of symptoms at the beginning of the intervention have an influence on the therapy outcome. We calculate this with a multiple regression with days of hospitalization and/or the PANSS total score as independent variables. The treatment outcome is defined as the delta between symptoms before and after the intervention and serves as dependent variable.

General statistical considerations: We will use routine procedures of data processing and use data transformation if necessary (in case of non-normal distribution). Standard statistical calculations will be computed. The level of significance will be set to  $p < 0.05$  (two tailed). Effect sizes will be calculated for significant results. The IBM® SPSS Statistics® statistical software as well as the program R will be used.

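### Hypothesis 3 concerns the time after discharge, but its two questionnaires are scheduled only at days 0 and 10, and the existing day-60 visit omits them

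*Combined protocol and SAP*

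**What the plan says.** Section 2.1 words Hypothesis 3 as "Patients show higher motivation to seek psychotherapeutic treatment and have a higher self-efficacy expectation after leaving the inpatient stay", and its third objective speaks of "higher expectations of self-efficacy after discharge from the hospital". Section 4.1 repeats the time frame: "have a higher self-efficacy expectation after leaving the inpatient stay".

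The instruments are the FPTM and the GSE, both secondary endpoints. On timing, Section 2.2 says: "All secondary variables will be measured before and after the study intervention or control intervention". Table 2 in Section 3.3 agrees: the row "Measurements of secondary outcome variables" is marked at Visit 2 (day 0) and Visit 7 (day 10) and has no mark at the follow-up on day 60 ± 5. The only row marked at follow-up is "Examination of symptoms with PANSS and MATRICS", which is also marked at days 0 and 10.

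On setting, Section 3.3 says that "the duration for each patient is between 13 and max. 16 days during their inpatient stay". On the calendar it says: "The survey phase will last until August 2023".

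Section 4.1 plans a baseline-adjusted ANCOVA for each hypothesis without naming an outcome time point. It mentions neither day 60 nor MATRICS. Its additional regression takes the pre-to-post change in symptoms as the outcome.

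**The concern.** The hypothesis and the schedule point to different times. Hypothesis 3 asks about patients who have left hospital, while its questionnaires are given at a visit that the plan places within the stay. A between-group difference at day 10 would show an effect at the end of four sessions. It would not show whether the effect is present after discharge, which is what the hypothesis states.

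A later visit already exists, but it collects symptom and cognitive data for which no analysis is stated. Patients would be asked to give up to 60 minutes at day 60 without the two measurements that Hypothesis 3 needs. Post-discharge measurements that are not taken cannot be recovered later.

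**Working it through.** **1. Where the FPTM and GSE measurements fall.** From the nominal days and windows in Table 2:

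- Visit 1 (day −3 ± 2) to Visit 7 (day 10 ± 1): nominal 10 − (−3) = 13 days; shortest 9 − (−1) = 10; longest 11 − (−5) = 16. The nominal and longest spans match the stated 13 and 16 days, so day 10 belongs to the period that the plan calls inpatient.
- Visit 1 to follow-up (day 60 ± 5): nominal 63 days; shortest 55 − (−1) = 56; longest 65 − (−5) = 70.
- Visit 7 to follow-up: nominal 50 days; shortest 55 − 11 = 44; longest 65 − 9 = 56.

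Day 60 is therefore the only visit scheduled beyond the declared inpatient period, and neither questionnaire is scheduled there.

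**2. The early-discharge exception.** Section 3.4 allows outpatient completion after at least three inpatient sessions. The third session is Visit 5 (day 6 ± 1). A patient using this route would be measured at most 10 − 6 = 4 days after discharge nominally, or 11 − 5 = 6 days with the windows.

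**3. Use of the day-60 data.** Three texts bear on this: the ANCOVA statements (no time point), the regression (pre-to-post change) and Section 2.2 (before and after the intervention). None assigns a role to day-60 PANSS. MATRICS tests bear on eligibility at baseline through the cognitive exclusion criterion in Section 3.1, but they have no endpoint or analysis at any visit.

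**4. The plan's sample size, then power at day 60.** Section 4.1 gives f = 0.25, 80% power, two-sided alpha 0.05 and N = 128. For two equal groups d = 2f = 0.5.

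- Normal approximation: n per group = 2(1.96 + 0.842)² / 0.5² = 62.8, so 63.
- Two-sample t-test: 63.8, so 64 per group and N = 128. The plan's figure reproduces.
- ANCOVA F test with one covariate, df 1 and 125, noncentrality 128 × 0.0625 = 8: power 0.801.

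No loss rate is given, so a range is assumed. With m = 128(1 − L)/2 per group, the two-sample t-test at d = 0.5 gives:

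| Assumed loss by day 60 | Per group | Power | N recruited to keep 128, 128/(1 − L) |
|---|---|---|---|
| 0% | 64.0 | 0.80 | 128 |
| 10% | 57.6 | 0.76 | 143 |
| 20% | 51.2 | 0.71 | 160 |
| 30% | 44.8 | 0.65 | 183 |
| 40% | 38.4 | 0.58 | 214 |

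**5. Calendar and burden.** For a nominal day-60 visit by 31 August 2023, baseline must fall by 31 August − 60 days = 2 July (27 June at day 65, 7 July at day 55). A day-10 visit by the same date needs baseline by 21 August, which is 50 days later. The six sessions in Section 6.1 equal pre-measurement, four interventions and post-measurement (1 + 4 + 1), so the follow-up is left out there as well as from the 13 to 16 days.

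**The case against.** **The hypothesis may be prospective.** Motivation to seek treatment and an expectation of self-efficacy can be voiced in hospital about the time after it. Section 2.2 fits that reading. This stands as a possibility, and it is why rewording is an acceptable alternative. The phrase about leaving the inpatient stay still favours measurement after discharge, and the text needs settling either way.

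**Some day-10 values may be post-discharge.** Section 3.4 does allow this, so a reader should not infer that the trial yields no post-discharge FPTM or GSE data at all. These values would come from an unplanned subset defined by early discharge, within days of leaving. They are not a planned test in all patients.

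**Day 60 may not be after discharge for everyone.** The documents give no length of stay. Day 60 is only the visit scheduled outside the declared inpatient period.

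**Two PANSS time points might suggest two chances at 0.05.** A reader could infer this because the Hypothesis 2 ANCOVA names no time point. The documents do not support it: no second PANSS test is planned, and Section 2.2 and the regression outcome both point to day 10. What is left is a missing statement, not demonstrated error inflation.

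**Day 60 is a weaker time point.** Section 4.2 analyses completers and excludes missing data, and Section 3.2 pays compensation after the post-measurement, not after follow-up. This stands as a cost of the fix.

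**Conclusion.** The point holds: by design, the plan does not test Hypothesis 3 at the time the hypothesis names. FPTM and GSE are measured at days 0 and 10 only. The visit scheduled 44 to 56 days after the post-measurement omits both and collects PANSS and MATRICS data with no stated analysis.

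This rests on reading the hypothesis as measurement after discharge, and on an absence: Section 4.1 does not bar use of the day-60 data, it just gives them no role. It would go too far to say that the trial cannot answer Hypothesis 3, given the outpatient exception and the prospective reading.

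The endpoints concerned are secondary, and the primary endpoints (STAR and BARS) are untouched. The change should be made before data collection. The power range of 0.76 to 0.58 is a cost of the preferred fix. It rests on assumed loss of 10% to 40%, no replacement of patients lost after day 10, d = 0.5, and no gain in precision from baseline adjustment.

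**What to change.** **Preferred.** Mark FPTM and GSE at the day-60 visit in Table 2 and amend Section 2.2 to match. In Section 4.1, name day 60 as the time point for Hypothesis 3, by ANCOVA on the day-0 score, with day 10 supportive.

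**Alternative.** If day-60 measurement is not feasible, reword Objective 3 and Hypothesis 3 in Sections 2.1 and 4.1 to the end of the intervention.

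**In either case:**

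- State that day 10 is the time point for Hypothesis 2 and that day-60 PANSS is supportive.
- State the purpose and analysis of MATRICS at day 60. The documents give no instrument timings, so there is no basis for removing it to make room.
- Count the day-60 visit in the duration in Section 3.3, in the sessions in Section 6.1 and in the calendar, with nominal baselines by about 2 July 2023 for visits by 31 August.

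**Cost.** Two more questionnaires, one of them with 39 items, at a visit already planned for up to 60 minutes. Attendance will probably be lower than at day 10, and complete-case analysis under Section 4.2 turns that directly into lost power. The plan should give an expected loss rate and the resulting power, and say whether the replacement rule in Section 3.4 covers patients who miss day 60. Rewording costs nothing in data but gives up the claim about the time after discharge.
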